8.2 EXCLUSION CRITERIA

A subject who meets any of the criteria listed below (in either eye) will be excluded from the study:

1. Any active, clinically significant ocular or peri-ocular infection or inflammation
2. Recurrent clinically significant eye inflammation, other than dry eye, within 3 months prior to enrollment
3. History of eyelid, conjunctiva or corneal surgery (including refractive surgery) within the past year. In addition, subjects with any history of the following are excluded: chalazion surgery, surgery on the tarsal conjunctiva, radial keratotomy (RK), complicated blepharoplasty, lid reconstruction, or significant complications post-refractive surgery.
4. Any office-based dry eye treatment (e.g. IPL, thermal pulsation [Lipiflow], etc.) within 12 months prior to enrollment. In addition Blephex or debridement within 3 months prior to enrollment is an exclusion.
5. Meibomian gland expression within 6 months prior to enrollment. In addition, any history of meibomian gland probing is an exclusion.
6. In the clinical judgement of the investigator, meibomian glands have significant capping, atrophy, or are unable to be expressed, digitally or with a sterile cotton swab.
7. Contact lens use within the past 2 weeks (Subjects must refrain from wearing contact lenses for the duration of the study.)
8. Use of TrueTear device within the past 2 weeks (Subjects must refrain from using the TrueTear device for the duration of the study.)
9. History of Ocular Herpes Simplex or Ocular Herpes Zoster
10. Clinically significant ocular surface abnormalities that may affect tear film distribution or treatment (e.g. pterygium, anterior membrane dystrophy, etc.)
11. Clinically significant eyelid abnormalities in either eye (e.g. entropion/ectropion, blepharospasm, aponeurotic ptosis, lagophthalmos, notching of lid margin, distichiasis, trichiasis)
12. Clinically significant anterior blepharitis. In addition, collarettes or flakes of more than one quarter of the eyelid are excluded.
13. Clinically significant dermatologic or cutaneous disease of the eyelid or periocular area

14. Ocular trauma within 3 months prior to enrollment
15. Any active, clinically significant allergic, vernal, or giant papillary conjunctivitis
16. Known history of diminished or abnormal facial, periocular, ocular or corneal sensation
17. Corneal surface abnormalities such as corneal epithelial defects (other than punctate staining), ulcers, corneal epithelial dystrophies, keratoconus, and ectatic disease of the cornea
18. Punctal occlusion or punctal plug placement within 30 days prior to enrollment
19. Systemic diseases resulting in dry eye (e.g. autoimmune diseases such as Sjogren's syndrome, rheumatoid arthritis, lupus, Graves' disease, sarcoidosis, etc.)
20. Allergies to silicone tissue adhesives
21. Use of Restasis or Xiidra within 60 days prior to enrollment. Subject must also be willing to remain off these drugs for the duration of the study.
22. Use of antihistamines (oral or topical) within 10 days prior to enrollment. Subject must also be willing remain off antihistamines for the duration of the study.
23. Subject is currently on a systemic medication(s) (other than anti-histamines) that is known to cause ocular dryness (e.g. diuretics, anti-hypertensives, anti-depressants, hormone therapy) and whose dose of this medication(s) has not been stable within 30 days prior to enrollment. There must be no anticipated adjustments to the dose of these medications for the duration of the trial.
24. Subject has taken or is currently taking Accutane
25. Subject requires chronic use (i.e. for any portion of the study) of topical ophthalmic antibiotics, anti-glaucoma medications, steroids, non-steroidal anti-inflammatory medications or who has been on any of these medications within 30 days prior to enrollment
26. Subject is currently using Retin A or Latisse
27. Participation in another ophthalmic clinical trial within one year prior to enrollment. Subject must also be willing to refrain from another ophthalmic study for the duration of the study.
28. Co-existing condition, either ocular or non-ocular that, in the judgement of the investigator could affect the safety or effectiveness of treatment or the compliance of the subject to the protocol. Subjects who are pregnant or nursing or have active, wet macular degeneration are excluded.

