20.2 MEDICATIONS

When recording medications that the subject is taking, be sure to ask the subject to list any over-the-counter medications and supplements they are taking that could affect dry eye disease including, for example, cold medicines, Benadryl, fish oil supplements and Omega 3 products, retinol products, Latisse, etc.

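### Exclusion 23 tests dose stability only in subjects still taking a drying systemic drug, so a subject who stopped one within the past 30 days is eligible

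*Combined protocol and SAP*

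**What the plan says.** Item 23 of section 8.2, repeated in the Synopsis, has two joined conditions. The first is "Subject is currently on a systemic medication(s) (other than anti-histamines) that is known to cause ocular dryness", with diuretics, anti-hypertensives, anti-depressants and hormone therapy as examples. The second is "and whose dose of this medication(s) has not been stable within 30 days prior to enrollment". A closing sentence rules out anticipated dose adjustments of the same drugs during the trial.

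Neighbouring items look back in time regardless of current use:
- Item 21: "Use of Restasis or Xiidra within 60 days prior to enrollment"
- Item 22: "Use of antihistamines (oral or topical) within 10 days prior to enrollment"
- Item 24: "Subject has taken or is currently taking Accutane"
- Item 25: a 30-day look-back for several topical ophthalmic drugs

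Item 26, like item 23, is in the present tense only: "Subject is currently using Retin A or Latisse".

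Section 20.2 (Appendix A) tells staff to ask about non-prescription drugs as well as "supplements they are taking that could affect dry eye disease including, for example, cold medicines, Benadryl, fish oil supplements and Omega 3 products". It also names retinol products and Latisse. This is an instruction for recording, not an eligibility rule.

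**The concern.** Item 23 protects the Baseline value: a subject whose exposure to a drying drug has just changed may not be at a steady state, so later change cannot be read as a response to treatment. Stopping the drug is as much a change in exposure as altering its dose, but the wording reaches only people who still take it.

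The design offers no second line of defence. There is no control arm (section 7), the effectiveness endpoints are mean changes from Baseline (section 6.1), and follow-up is at Days 5–9 and 21–35 (Table 2). Recovery in that period after a drying drug is withdrawn would go into the reported mean with nothing to separate it from the procedure.

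**Working it through.** **Step 1. Apply item 23 as written.** The intervals are illustrative.

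| Subject at Baseline | Currently on the drug? | Dose unstable within 30 days? | Result under item 23 |
|---|---|---|---|
| Same dose for more than 30 days | Yes | No | Admitted |
| Dose changed 10 days ago | Yes | Yes | Excluded |
| Started 10 days ago | Yes | Yes, on the natural reading | Excluded |
| Stopped 5 days ago | No | Not tested | Admitted |

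Only the last row conflicts with the item's purpose. The gap is therefore about stopping; starting is plausibly caught already.

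**Step 2. Look for another provision that closes it.**
- Items 22 and 24 cover antihistamines and Accutane, not the drug classes in item 23.
- Item 28 concerns a co-existing condition, not a recent medication change.
- Section 9.5.4 restricts what subjects use after treatment. It cannot reach a drug stopped before Baseline.
- Section 12.5 removes major protocol deviations and names Xiidra and Restasis. A subject who meets the criteria as written has not deviated.
- Section 12.7 allows basic descriptive statistics only, with no adjustment or sensitivity summary for medication changes.
- Section 20.2 asks what the subject is taking, so a recently stopped drug may not be recorded and the subject may not be identifiable later.

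None of these closes the gap.

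**Step 3. Size.** The plan has no figure to reproduce: section 12.2 states that no sample size was calculated. If k of N subjects each gain d from the stopped drug, the mean change shifts by k × d / N. N = 30 is the ceiling in section 9.2. Both k and d are assumptions.

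Reference changes from the pilot (Table 1, Baseline to 4 weeks):
- TBUT: 14.8 − 3.1 = 11.7 s, matching the text of section 5.2
- OSDI: 41.0 − 15.7 = 25.3 points

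| Assumption | Shift | Share of pilot change |
|---|---|---|
| k = 2, d = 2 s | 2 × 2 / 30 = 0.13 s | 1.1% |
| k = 5, d = 2 s | 5 × 2 / 30 = 0.33 s | 2.8% |
| k = 9, d = 3 s (wide case) | 9 × 3 / 30 = 0.90 s | 7.7% |
| k = 2, d = 10 points | 2 × 10 / 30 = 0.67 points | 2.6% |
| k = 5, d = 10 points | 5 × 10 / 30 = 1.67 points | 6.6% |
| k = 9, d = 15 points (wide case) | 9 × 15 / 30 = 4.5 points | 17.8% |

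For comparison, taking the pilot's SD of 2.6 s for TBUT change as a between-subject SD (its table is per eye), the standard error of a mean of 30 is 2.6 / √30 = 0.47 s. The shifts for k = 2 to 5 lie below one standard error. The wide case, 0.90 s, is about 1.9.

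**The case against.** The strongest reply is that little depends on this. The study is exploratory, with no hypothesis (12.1) and no pass/fail criterion (12.3), so no decision rule exists for a small shift to tip. Attribution is weak in any uncontrolled design, and rewording one criterion does not cure that. Subjects must also show gland obstruction in both eyes and regular lubricant use over the past month (inclusions 3 and 6), which makes a purely drug-induced picture less likely. All of this stands and limits the weight of the point. None of it changes what item 23 says.

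A reader might also infer more than the documents support:
- **That item 23 bars all current users.** It does not. It admits those on a stable dose.
- **That a subject who has just started Omega 3 would inflate the device effect.** Section 20.2 says only that such products could affect dry eye disease. It does not say that they help, or how fast. Section 9.5.4 bars other methods of relieving symptoms during follow-up in an open-ended list, which can be read to include Omega 3 taken for that purpose, although supplements are not named.
- **That stopping Retin A or Latisse biases the result in the device's favour.** Item 26 does lack a look-back, but the documents give no direction of effect.

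For item 23 the direction, though not the timing or size, follows from the protocol's own description of these drugs as causing dryness.

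**Conclusion.** The point holds for item 23. Read literally, it admits a subject who stopped a drying systemic drug within the 30 days over which it requires stability from everyone still taking one. If recovery follows within the study period, it is counted as device effect.

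The size cannot be derived from the documents. It rests on the assumed k and d, on N = 30, and on the recovery falling between Baseline and Day 35; a smaller per-protocol set would raise the shift in proportion. With 2 to 5 affected subjects the shift is about 1–3% of the pilot change for TBUT and 3–7% for OSDI. That would not account for an effect of the size seen in the pilot. The reason to act is that the criterion misses subjects it was written to screen out and is cheap to correct.

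Item 26 and the supplements named in section 20.2 raise a consistency question only.

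**What to change.** In section 8.2 and the Synopsis, reword item 23 so that its existing 30-day test excludes anyone who has started, stopped or changed the dose of a drying systemic medication in that period. Leave the sentence on anticipated adjustments in place.

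Keep the carve-out for antihistamines. Without it, a subject who stopped an antihistamine 15 days before enrollment would pass item 22 (10 days) and fail item 23 (30 days). For the same reason, do not import the list in section 20.2 into item 23, since it names Benadryl and cold medicines.

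Add a question to the Baseline medication history on such drugs stopped in the past 30 days.

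The cost is one look-back question, revised wording in two places and on any eligibility worksheet, and a few more screen failures or short enrollment delays.

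Separately, the sponsor should reconcile item 26 and section 20.2 with the look-backs in items 21, 22 and 25 and with section 9.5.4, and state how supplements are handled. Whether those products need a window, and how long, is the sponsor's choice.

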9 STUDY PROCEDURES

9.1 STUDY SCHEDULE

The Study Schedule is shown below in Table 2.

Table 2: Study Visit Schedule

Visit (Visit Window)	Baseline (Day 0)	Wk 1 (Day 5-9)	1 Mo (Day 21 – 35)
Informed Consent	X		
Demographics, Ocular & Medical History	X		
Medication use	X	X	X
OSDI*	X	X	X
Best Spectacle corrected visual acuity (Snellen)*	X	X	X
Slit Lamp Exam*	X	X	X
Tear Breakup Time*	X	X	X
Corneal Staining*	X	X	X
Conjunctival Staining*	X	X	X
Meibomian Gland Secretion Scoring*	X	X	X
TearCare Treatment	X		
AE Assessment*	X	X	X
Lubricant Drops Log			X

* Endpoint assessment should be performed by an independent study staff who does not perform the TearCare procedure on study subjects.

9.2 NUMBER OF SUBJECTS AND DURATION OF FOLLOW-UP

Up to 30 subjects will be enrolled and treated in the study. All subjects will be followed for 1 month.

9.3 MATERIAL AND EQUIPMENT

A listing of general equipment and materials required at the investigational site for the study is provided below.

- TearCare System (including a SmartHub, SmartHub Nest, and charging adapter)
- TearCare iLid Devices and Physician Gland Clearing Devices
- Snellen Visual Acuity System
- Wratten filter (yellow)
- Meibomian Gland Evaluator (TearScience, Inc.)
- Fluorescein sodium strips or compounded fluorescein (0.5 – 2%) preservative-free ophthalmic solution
- Lissamine green strips
- 0-10µL & 20-200 uL micropipettes and sterile tips
- Microcentrifuge tubes
- Preservative-free sterile saline
- Proparacaine 0.5% or tetracaine 0.5% ophthalmic drops
- Akten® (lidocaine hydrochloride ophthalmic gel) 3.5% or equivalent

- Stopwatch
- Makeup remover wipes
- Sterile scissors

9.4 INFORMED CONSENT AND POINT OF ENROLLMENT

The IRB-approved informed consent will be presented and explained to each prospective subject by the investigator or a trained clinical professional. Once the subject has had ample time to read the consent form, has been informed of all aspects of the study, and has had an opportunity to ask questions, the subject will be given a choice to voluntarily confirm his or her participation in the study as documented by completion of the Informed Consent. After signing the Informed Consent and the HIPAA (Health Insurance Portability and Accountability Act) authorization, the subject can then proceed with the baseline visit. The subject has the right to withdraw from the study at any time without consequences, as indicated in the Informed Consent Document.

The subject's signed and dated informed consent must be obtained before conducting any procedure specifically for the study. Subjects are enrolled upon signing the ICD even if they subsequently fail to meet the eligibility criteria.

The principal investigator(s) must retain the original, signed written Informed Consent Document. A copy of the written Informed Consent Document must be given to the subject.

9.5 BASELINE VISIT

9.5.1 SCHEDULING THE BASELINE VISIT

Since dry eye drops and lubricants can affect the endpoint assessments, instruct subjects not to use any of these products within 2 hours of the Baseline visit.

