9.5.2 BASELINE EXAMS AND QUESTIONNAIRES

After the subject has signed the informed consent form and agreed to participate in the study, the exams, tests and questionnaires listed in the Baseline column of Table 2 should be performed. Refer to Appendix A for instructions for performing the exams and administering the questionnaire.

At this visit, subjects should undergo the following tests and exams, performed in the order indicated below, to screen them for the study qualification and to record baseline data. Endpoint assessments (indicated with a *) should be performed by independent study staff who does not perform the TearCare procedure on study subjects.

1. OSDI Questionnaire
2. Demographics, medical and ocular history
3. Medication use: ocular and systemic
4. Best-spectacle corrected visual acuity*
5. Slit Lamp Exam*
6. Tear Breakup Time*
7. Corneal staining*
8. Conjunctival staining*
9. Meibomian Gland Secretion Scoring*

If, at any point during the visit the subjects fails to meet a subject selection criterion, then the visit can be terminated. Subjects who fail to meet all the selection criteria will be considered a screen failure and will be withdrawn from the study. Screen failures will not count toward the total enrolled and treated number of subjects.

NOTE: Questionnaire and exam data collected on subjects prior to enrollment as part of the routine clinical practice may be used to pre-screen patients for the study. However, once the subject signs the consent form and is enrolled in the study, these questionnaires and exams must be repeated following the protocol procedures.

After all required measurements have been obtained and it has been confirmed that the subject meets all the Subject Selection Criteria, then the subject will receive the TearCare procedure.

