9.5.4 MANAGEMENT OF DRY EYE SYMPTOMS DURING FOLLOW-UP

During follow-up, if subjects require relief of their dry eye symptoms, they should only use Refresh® Plus drops. Other types of over-the-counter lubricants should not be used. Subjects should record their daily use of lubricants on the Lubricant Drop log.

Subjects **should not use** any other method of relieving dry eye symptoms, including any of the following:

- Warm compress
- Restasis or Xiidra
- Other dry eye treatments (e.g. Lipiflow, TrueTear, iLux, punctal plugs, etc.)
- Lubricants other than Refresh Plus

NOTE: If a subject had a punctal plug at the baseline visit and it falls out during the study, it should be replaced.

Review these instructions with subjects at the end of the Baseline visit and provide them with the Lubricant Drop log. They should complete the log each day and bring it back to the clinic at the 1 month follow-up visit.

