9.6 FOLLOW-UP VISITS

Prior to the Visit: Reminder Call

Since dry eye drops and lubricants can affect the endpoint assessments, it is important to call subjects a few days before their follow-up visits to remind them that on the day of the Follow-up visit, they should not to use any of these products before the Follow-up visit.

Order of Procedures During the Follow-Up Visit

Follow-up exams should not be performed by the clinician who performed the TearCare procedure.

Follow-up procedures will be performed per the Study Schedule provided in Table 2 (page 25) and the methods included in Appendix A. Since certain tests/exams can impact the ability to perform other tests/exams, the following tests and exams should be performed in this order:

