14.3 SOURCE DATA AND CASE REPORT FORMS

Data will be collected directly on the study worksheets provided by the sponsor and these study worksheets will serve as the source data.

Source data and study worksheets are to be maintained at the site in the subject records or in the medical records. All entries must be made in black or blue ink and changes must be made by strike-through only with date and initials or signature. All source documents must be completed and signed by the authorized study personnel (e.g., study coordinator). No "white-out" is to be used on the source documents.

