20.4 TEAR BREAKUP TIME (TBUT)

TBUT is an indicator of tear film instability.

Methods for Preparing and Administering Fluorescein into the eye

Any of the following methods may be used to administer fluorescein into the subject's eye. Whenever possible, the same method should be used for follow-up visits that was used for the baseline visit for a particular subject. In addition, whenever possible, the same method should consistently be used at a site on all subjects.

1. DET Strips:

[figure not shown]
The Dry Eye Test (DET) method should be followed using DET test strips (Amcon Laboratories). While holding a fluorescein impregnated DET strip suspended in air, use a micropipette to apply 10uL of sterile saline onto the dyed end of the strip. Do not allow the saline to drip off and do not shake the strip. Instill the dyed tip of strip into the lower conjunctival fornix.

2. Compounded Fluorescein Solution

Obtain 0.5%, 1.0% or 2.0% preservative-free fluorescein ophthalmic solution from a compounding pharmacy. Using a micropipette, instill 5uL of the solution into the lower conjunctival fornix.

3. Prepare Fluorescein Solution Per the Gyau Method²⁹

- a) Put on a pair of sterile gloves.
- b) Cut three (3) 1.0 mg Fluorescein Sodium Ophthalmic strips at the end of the colored portion of the strip using sterile scissors and tear each portion into 3 pieces. You should have 9 pieces.

- c) Place the 9 pieces into a disposable microcentrifuge tube. Make sure the pieces of the strips are lying at the bottom part of the tube. Pipette 200 μ L of sterile saline into the tube containing the cut strips. Gently shake the tube to make sure the fluid is covering all the pieces of the cut strips and cover with the lid.

- d) Wait 3-15 minutes before using the Fluorescein solution.
- e) Using a micropipette, instill 5 μ L of the solution into the lower conjunctival fornix.
- f) After use, discard the remaining solution and microcentrifuge tube.

Measuring Tear Breakup Time

Under the cobalt blue illumination of the slit lamp, tear break-up time should be assessed. Tear Break-up Time is defined as the number of seconds between a blink and the appearance of a first dry spot or negative staining in the tear film.

[figure not shown]

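### The lubricant-free interval is 2 hours before Baseline but the whole day before Week 1 and 1 Month, so change from baseline in TBUT and staining is measured under two instructed conditions

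*Combined protocol and SAP*

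**What the plan says.** Section 9.5.1 (Scheduling the Baseline Visit) tells sites to "instruct subjects not to use any of these products within 2 hours of the Baseline visit". Section 9.6 (Follow-up Visits) has sites telephone subjects a few days ahead to remind them that "on the day of the Follow-up visit, they should not to use any of these products before the Follow-up visit". Both sections justify the rule in the same way: drops and lubricants may influence the endpoint measurements. Section 9.6 covers both Week 1 and 1 Month.

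Other relevant text:

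- Section 6.1 defines the primary endpoint (TBUT) and the corneal and conjunctival staining endpoints as mean changes from baseline. Section 7 describes a single-arm study.
- Section 8.1 requires regular use of artificial tears or lubricants over the past month.
- Appendix A, section 20.4, says of fluorescein: "Whenever possible, the same method should be used for follow-up visits that was used for the baseline visit for a particular subject".
- Table 2 lists "Medication use" at all three visits. Section 9.5.2 specifies "Medication use: ocular and systemic" at Baseline, and section 20.2 tells staff to "be sure to ask the subject to list any over-the-counter medications and supplements they are taking that could affect dry eye disease".
- Section 9.5.4 restricts lubricants during follow-up to one product and says "Subjects should record their daily use of lubricants on the Lubricant Drop log".
- Section 12.7 plans basic descriptive statistics only, and section 12.3 sets no pass/fail criteria.

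**The concern.** A change from baseline is interpretable when both measurements are taken under the same conditions. Here the sponsor names lubricant use as something that can disturb the assessments, then controls it less strictly at Baseline than at follow-up and gives no reason for the difference. Section 20.4 shows that like-for-like TBUT measurement was an aim, at least for the dye method, but the aim was not carried over to lubricants.

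A concurrent control arm would face the same two rules, and much of any shift would cancel in the comparison. With one arm it stays in the estimate. If residual lubricant lengthens TBUT (an assumption), the looser Baseline rule would raise baseline values and understate the improvement; if it shortens TBUT, the improvement would be overstated. The same reasoning applies to the staining scores.

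**Working it through.** **Is there a reconciling rule?** Table 2, sections 9.5.2 and 9.5.4, and Appendix A give no lubricant-free interval for TBUT or staining. Only 9.5.1 and 9.6 do, and they differ. No section asks for the time of the last drop.

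**How far apart are the instructions?** The documents give no appointment times and do not say when the day begins. Assume visits at 09:00, 11:00 or 14:00, and a day starting at midnight (calendar day) or at 07:00 (waking). Minimum interval at follow-up = visit time − start of day. Excess over Baseline = that interval − 2 h.

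| Visit | From 00:00: minimum (excess) | From 07:00: minimum (excess) |
|---|---|---|
| 09:00 | 9 h (7 h) | 2 h (0 h) |
| 11:00 | 11 h (9 h) | 4 h (2 h) |
| 14:00 | 14 h (12 h) | 7 h (5 h) |

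For a 14:00 visit, a drop at 11:30 complies at Baseline and breaks the rule at Week 1 and 1 Month. On the calendar-day reading the two rules would coincide only for a visit at about 02:00.

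**What could this do to the primary endpoint?** The documents give no lubricant effect on TBUT beyond 2 hours, so only a range can be shown. Shift in mean change = share of subjects whose actual intervals differ × TBUT effect in those subjects. Shares and effects are assumed. The yardstick is the 1-month TBUT change of 11.7 s (SD 2.6 s) in the pilot study summarised in section 5.2.

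| Assumed effect | Shift at 50% share (% of 11.7 s) | Shift at 100% share (% of 11.7 s) |
|---|---|---|
| 0 s | 0 s (0%) | 0 s (0%) |
| 0.25 s | 0.125 s (1.1%) | 0.25 s (2.1%) |
| 0.5 s | 0.25 s (2.1%) | 0.5 s (4.3%) |
| 1 s | 0.5 s (4.3%) | 1 s (8.5%) |

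**How does that compare with sampling error?** Taking the pilot SD as a per-subject SD and the maximum of 30 subjects (section 9.2):

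- SE = 2.6/√30 = 0.475 s.
- 95% half-width = t(0.975, 29 df) × SE = 2.045 × 0.475 = 0.97 s.
- Shift ÷ half-width: 0.25/0.97 = 0.26; 0.5/0.97 = 0.52; 1/0.97 = 1.03.

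The plan does not call for a confidence interval; the half-width is used here only as a scale. It is approximate, because Table 1 reports 24 eyes from 12 subjects, so the SD may be per eye, and because the per-protocol population may number fewer than 30. The pilot also used 12 minutes of heating rather than 15, and different entry criteria.

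**The case against.** The strongest reply is that no harm is demonstrated. The difference matters only if lubricants still act on TBUT or staining more than 2 hours after use, and nothing in the documents says they do. By choosing 2 hours at Baseline the sponsor may have judged that long enough. The figures in seconds restate assumed inputs and do not estimate a bias. This stands: the size is unknown and may be zero.

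Actual exposure may also coincide. Two hours is a minimum, and regular use over a month need not mean use on the morning of a visit. This stands too, but no section asks for the time of last drop, so the documents give no means of showing that it did. The worksheets might: section 14.3 says "Data will be collected directly on the study worksheets provided by the sponsor and these study worksheets will serve as the source data", but neither they nor the log layout are shown, so whether they hold a time field cannot be determined.

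A lighter rule before Baseline may be deliberate, because subjects are asked to abstain before they have signed consent. That is reasonable, but the protocol does not say so, and it would not prevent using the 2-hour rule at follow-up.

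The fluorescein comparison is a soft one, since that request is qualified and three methods are allowed. It shows a preference for consistency, not a strict standard.

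Finally, the study is exploratory, and the inability to isolate the device effect comes from the single-arm design in general. That limits the importance of the point. It is not a reason to leave in place an avoidable difference between visits.

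**Conclusion.** The concern holds, as a minor comparability flaw. That the instructed conditions differ is certain from the text. Whether the difference biases the endpoints, and in which direction, cannot be determined from the documents.

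Under the assumptions shown, the instructed excess at follow-up runs from 0 to 12 hours. The illustrative shift in mean TBUT change runs from nothing to about the width of the study's sampling error, and stays small beside the pilot change. No decision rests on a threshold, so the consequence is confined to how the descriptive estimates of change in TBUT and staining are read.

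**What to change.** State one identical lubricant-free interval in 9.5.1 and 9.6 for Baseline, Week 1 and 1 Month. Either rule would serve:

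- **Two hours at every visit.** This adds no abstention before consent, but permits drops closer to the follow-up measurements.
- **None that day at every visit.** This is cleaner for measurement, but asks regular lubricant users to abstain longer before they have consented. The start of the day should then be defined.

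Record the time of last drop at each of the three visits and summarise the interval by visit. If the lighter Baseline rule is intended, state the reason and still record the time.

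The cost is one sentence in 9.5.1 or 9.6 and one worksheet item per visit, with no added visits or subjects. Equal intervals would not equalise the product used, because the restriction to Refresh Plus applies only during follow-up.
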